RC_04	Biological hazards	Exposure to biological hazards from collection of pathology samples. Clinical staff are exposed to body fluids during the delivery of treatment and collection of biological samples.	Risk for transmission of infectious diseases	Research Risk	Moderate	Possible	Medium	
 Staff appropriately trained and qualified to undertake phlebotomy Staff to follow standard and transmission based precautions, utilising supplied PPE, as required when conducting participant clinical assessments Sharps containers are located in prominent clinical areas Biological hazard bins are located in clinical areas Safety precautions and training for staff transporting blood to UnISC laboratories. Staff/students/participants to be advised not to attend the Thompson Institute when they have signs & symptoms of illness or infection, including, but not limited to illnesses such as Influenza, COVID, and suspected gastroenteritis. 	Personal Protective Equipment	Effective	Director, Thompson Institute	Manager, Clinical Programs	Minor	Rare	Low	
RC_05	Scheduling of assessments and interventions	Research participants require assessments and interventions as part of the research program. This includes time in dedicated clinical and research spaces that are used for other research and clinical programs at the TI	Assessments and interventions may not be completed within the allocated time frame, or completed at all due to competing priorities. Availability of space, access to medical equipment, availability of qualified staff to complete assessments and interventions, and availability of research participants may compromise this.	Research Risk	Major	Possible	High	
 A centralised booking system is available for the scheduling of MRI, EEGs and testing done in laboratories The TI have developed Research Operations forums to discuss research throughput and long-term planning of research programs Weekly research program meetings occur to discuss progress of clients through clinical assessments and interventions Qualified clinicians and technicians are employed who can conduct assessments within an allocated appointment time 	Administrative	Partially Effective	Director, Thompson Institute	Manager, Clinical Programs	Moderate	Possible	Medium	Require a mechanism that allows the monitoring in progress of research programs. To be discussed at the next Research Committee Meeting
RC_09	Negative health consequences to participants as a result of exposure to treatments	Drugs, medications and interventions administered to participants as part of the clinical trial.	Participant experiences negative or unexpected side effects, participant experiences negative health outcome (short or long-term), patient will not/cannot continue in trial, potential for UnISC reputation to be impacted	People Risk	Major	Possible	High	
 Ethical approval and compliance throughout the trial process Governance checklists and Operational Manual implemented and maintained. NPRC clinical staff (medical officers and Registered Nurses) who are working with participants have completed and update-to-date CPR and anaphylaxis training. Clinic to operate during business hours when SafeUnISC Officers are available to provide emergency response support, including advanced first aid. Clinical elements of the trial (i.e. heart rate monitoring, psychiatric scales, screenings) will be conducted by clinical staff who have received clinical certifications (i.e. registered nurse, doctor) Participants will undergo safety monitoring (i.e. physical assessments, suicidality monitoring) throughout the trial. Participants will be withdrawn from the trial if they fall outside of the safety parameters Rescue medication for client trial management available on site for administration by clinicians. Emergency portable Oxygen available on site, in the clinic and with SafeUnISC officers. AED available within the NPRC clinic. 	Personal Protective Equipment	Effective	Director, Thompson Institute	Manager, Clinical Programs	Minor	Unlikely	Low	
RC_10	Participant does not attend or is late for allocated assessment procedure	Various reasons outside TI control including failure to attend, not wanting to attend appointment, bad traffic, personal factors	Researchers and rooms booked and no longer required, reschedule required, or loss of data for that time point if unable to reschedule	Research Risk	Moderate	Likely	Medium	
 A protocol will be developed for managing cancellations including actions to take when a participant misses an appointment. Contact participant to check in and reschedule appointment. Participant will continue to be invited to future assessments unless they request to be withdrawn from the study or are outside of the assessment timeframe outlined in the project protocol Participants go through a screening process prior to the start of the study 	Administrative	Effective	Director, Thompson Institute	Manager, Clinical Programs	Moderate	Unlikely	Medium	
RC_11	Access to restricted drugs is compromised	Lack of security, processes or staff error	Medico-legal implications, inability to deliver treatment/research medication, loss of control of restricted substance, legal implications, require contact to police	Research Risk	Moderate	Possible	Medium	
 All Scheduled medications stored in accordance with the Medicines and Poisons Act 2019 (Queensland) the Medicines and Poisons Regulation 2021 (Queensland), and the Thompson Institute Substance Management Plan Regulated Medicines. A drug register will be maintained and regular audits of compliance regulations will be conducted in accordance with the Thompson Institute Substance Management Plan Regulated Poisons, Queensland legislation and regulations. The register will be stored in accordance with UnISC data safety policy and requirements of the Information Privacy Act 2009 - Queensland legislation. Any unused Investigational Product drug that is on-site at the end of the trial will be returned to the dispensing pharmacy for disposal. 	Administrative	Effective	Director, Thompson Institute	Manager, Clinical Programs	Moderate	Possible	Medium	
RC_12	Participant requests continued access to Psychology Services or medication on completion of trial	Perceived lack of effectiveness of trial treatment	Legal implications, medical implications in that ongoing treatment may be warranted, participant becomes dependant on trial staff and interventions	People Risk	Moderate	Likely	Medium	
 If a participant wishes to continue using a trial drug, the participant is to be advised that this can be discussed with their treating medical practitioner or psychiatrist. Reconciliation therapy success cannot be guaranteed. A pathway to second and third-line treatments, such as EMDR, CBT can be offered within the Clinic and/or referral to external mental health services for participants who do not benefit from Reconciliation Therapy. During the final Reconciliation Therapy visit, the Clinical Psychologist/Clinical team will discuss perceived benefit and options for follow up treatment with the participant. Oversight of participants entering continued therapy following Reconciliation Therapy is retained by the Clinical Governance Committee. 	Administrative	Effective	Director, Thompson Institute	Manager, Clinical Programs	Moderate	Unlikely	Medium	Require a Risk Treatment Plan. This will be managed by the Data & Therapeutics Committee

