4.3 Research Questions

1. Primary question: Will a 6-session reconsolidation blockade treatment be efficacious in reducing core PTSD symptoms frequency and severity.
2. Secondary question: Are there psycho-social, cognitive, and biological markers (genetic, circulating, and neural) that can predict treatment response to reconsolidation blockade treatment?

5. Project Design

	Screen	T1 Baseline Week 0	T2 Pre-treatment (after 4-week waitlist)	Intervention Weeks 1–6	T3 Post-treatment Week 7 or 8	T4 Follow up 1 1-month	T5 Follow up 2 3-month
Research Activity	30-min phone call	4-hour clinical assessment: Medical ax* Psycho-diagnostic ax Heart rate variability Substances screen Self-report measures - PDI - PDEQ - PCL-5 - IES-R - BDI-I - PTGI	4-hour clinical assessment: MRI CANTAB Biological ax Hair Clip Self-report measures -PCL-5 -IES-R -BDI-I - Any sig. changes from T1?	50-min RT session in week 1 Thereafter once weekly 25-minute RT sessions in weeks 2-6 Saliva IES-R	4-hour clinical assessment: MRI CANTAB Psych interview Biological ax Self-report measures - PCL-5 - IES-R - BDI-I - WHOQOL - PSQI	50-min clinical interview Self-report measures -PCL-5 -IES-R -BDI-I	4-hour clinical assessment: MRI CANTAB Psych interview Biological ax Hair clip Heart rate variability Substances screen Self-report measures -PCL-5 -IES-R -BDI-I -PTGI

		- ITQ - CTQ - WHOQOL - PSQI Eligibility met/not met					-WHOQOL - PSQI
Setting	Tele-health	UniSC	UniSC	UniSC	UniSC	Telehealth	UniSC
Participants	>18yro Diagnosed PTSD	>18yro Diagnosed PTSD	>18yro Diagnosed PTSD	>18yro Diagnosed PTSD	>18yro Diagnosed PTSD	>18yro Diagnosed PTSD	>18yro Diagnosed PTSD
Identifiability during data collection	Identifiable	Identifiable	Identifiable	Identifiable	Identifiable	Identifiable	Identifiable
Identifiability during data storage	Re-identifiable	Re-identifiable	Re-identifiable	Re-identifiable	Re-identifiable	Re-identifiable	Re-identifiable
Identifiability at the time of publications	Non-identifiable	Non-identifiable	Non-identifiable	Non-identifiable	Non-identifiable	Non-identifiable	Non-identifiable
Recruiting methods	-Social media -Flyers -Website -Email circulated to referral networks	n/a	n/a	n/a	n/a	n/a	Email/phone call to previous participants who consented to future contact
Consent	Verbal via survey question	Written Unspecified Written consent requested to contact for future projects	Verbal	Verbal	Verbal	Verbal	Verbal

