5.1 Methodological Approach

In this study, participants will receive manualised (Brunet & Lonergan, 2010) propranolol-based reconsolidation blockade treatment (hereafter called RT) once per week for six weeks in a single treatment arm. Each RT session will be conducted by trained practitioners. Session 1 will last 50 minutes while Sessions 2-6 will last 25 minutes and involve a script recall exercise to activate the specific trauma memory targeted for that session. Participants will be instructed to take the study oral medication (1mg/kg according to ideal weight) 60 minutes with a light snack before each scheduled RT session (i.e., 6 once-a-week doses over 6 weeks). The first dose will be taken on site under supervision of a registered nurse with access to a medical doctor. Subsequent doses will be taken at home before each treatment session. On the day of the first propranolol administration, the research trials

physician (GP) will be on-site to monitor for potential hypotensive events and ensure participant safety. This protocol builds on previous propranolol research and aligns with memory reconsolidation theory principles.

Throughout the study, participants will remain under the care of their existing treating team (i.e. medical practitioner, psychiatrist and/or psychologist), who will oversee any modifications to their existing treatments. RT will be used as an adjunctive treatment, allowing participants to maintain their current psychotropic medications, if any, under their physician's guidance. Any changes in medication will be documented by the study staff. It will be strongly recommended to participants and their treating team to not commence any new mental health treatments during the clinical study.

The primary outcome of the study is a change in PTSD symptomatology, assessed using the battery of psychological assessments (i.e., PCL-5, structured clinical interview) at several time points:

- T1 Baseline assessment (week 0)
- T3 post-treatment assessment (week 7 or 8)
- T5 Follow-up 2 (3 month)

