- Pre-assessment self-report questionnaire pack, including demographic questions (see Appendix E for examples questions).

Medical assessment

A medical assessment will be conducted by the study physician onsite to evaluate potential participants' health status. This assessment will screen for any significant medical health concerns (past or present), drug and alcohol use, heart rate variability, comorbid diagnoses, current medication use, and determine if there are any contraindications to the use of propranolol. The assessment will also consider any history of adverse reactions to propranolol, as well as conditions such as asthma, low blood pressure, diabetes, or cardiac concerns. This information will help determine if a potential participant is eligible to safely participate in the study or if they should be referred back to their treating team in the community. For more detailed information, please refer to the physical health assessment in Appendix D.

Pre-treatment self-report questionnaire pack

All potentially eligible participants will be required to complete a series of self-report measures prior to their in-person assessments. Potential participants will be sent a digital link via email for the *pre-treatment self-report questionnaire* pack which will include the following demographic and self-report questionnaires (See Appendix E for full details):

Demographic questions

- Date of birth
- Sex
- Contact details
- Emergency contact information
- Employment status
- Education level
- Current and past medications taken
- Current and past medical history

Self-report questionnaires

- **Peritraumatic distress inventory (PDI):** 13-item scale measures the level of distress experienced by an individual during and shortly after a traumatic event.
- **Peritraumatic dissociative experiences questionnaire (PDEQ):** 13-item self-reporting scale that assesses an individual's emotional reactions at the time of or immediately after a traumatic event.
- **PTSD Checklist for DSM-5 (PCL-5):** 20-item self-report measure that assesses the 20 DSM-5 symptoms of PTSD.
- **The Impact of Events Scale – Revised (IES-R):** 22-item measure of the subjective response to a specific traumatic event in an adult or senior population.
- **Beck Depression Inventory (BDI-I):** 21 item self-report scale designed to measure the negative emotional states of depression.

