The project lead will coordinate with each participant to attend a session at Week 7 or 8 to collect post-treatment assessment measures. See Table 1 for specific assessments completed during this stage.

Follow up 1 (T4) 1 month

The project lead will coordinate with each participant to attend the follow up 1 telehealth session, which will take 50 minutes. This will involve a clinical interview and psychological measures (PCL-5, IES-R, and BDI-I).

Follow up 2 (T5) 3 month

The project lead will coordinate with each participant to attend the 3 month follow up assessment taking approximately 4 hours in total. See Table 1 for specific assessments completed at this stage.

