5.9 Data Collection/Gathering

The study will be collecting mental health information, biospecimens and neurological information of its participants. Collection will take place on site at the UniSC Thompson Institute campus by trained research personnel. The RPIS, consent form, and questionnaire measures will be created in and delivered via Qualtrics, using the research team's password protected UniSC Qualtrics account. Qualtrics is a UniSC approved site and stored survey answers can only be accessed using the researcher's password-protected USC-Qualtrics account.

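### The T3 and T5 PCL-5 is planned for an attended on-site session, and no remote fallback is stated if that visit is missed

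*Protocol*

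**What the plan says.** Section 5.1 defines the primary outcome: "The primary outcome of the study is a change in PTSD symptomatology, assessed using the battery of psychological assessments (i.e., PCL-5, structured clinical interview"), measured at T1, T3 (week 7 or 8) and T5 (3 months). T4 is not on that list.

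The schedule table under section 5 places the T3 PCL-5 inside a long visit: "4-hour clinical assessment: MRI CANTAB Psych interview Biological ax Self-report measures - PCL-5". The setting row for T3 and T5 is UniSC, and T5 is also a visit of about 4 hours. Section 5.4 says of T3: "The project lead will coordinate with each participant to attend a session at Week 7 or 8 to collect post-treatment assessment measures". Section 5.9 states in general terms: "Collection will take place on site at the UniSC Thompson Institute campus by trained research personnel". The same section says that the questionnaires are delivered through Qualtrics.

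Two other time points use a remote route. Before T1, section 5.4 says "Potential participants will be sent a digital link via email for the" pre-treatment questionnaire pack, which contains the PCL-5. For T4 it says "The project lead will coordinate with each participant to attend the follow up 1 telehealth session, which will take 50 minutes", and the PCL-5 is among the measures taken then.

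For a missed or late assessment, Appendix L, RC_10 lists as an implication rescheduling or "loss of data for that time point if unable to reschedule". Its controls are contact to rebook, continued invitation to later assessments within the protocol's timeframe, and a cancellation procedure still to be written.

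**The concern.** A short self-report form carries half of the primary outcome definition, yet at the two time points that matter most it is planned alongside MRI, cognitive testing, an interview and biological sampling. Anyone who cannot or will not attend that visit may also miss the form, even though the form can be answered from home.

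The study has a single arm, so no comparison group offsets selective attendance. If those who miss the visit have improved less, the mean change among attenders overstates the benefit. Section 5.10 promises intent-to-treat analysis, but imputation there is optional and conditional on an ignorable missingness pattern. Unwillingness to attend, which RC_10 lists among the causes, may not meet that condition. An analysis plan can model missing data but cannot collect them, so this is a matter for the protocol.

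**Working it through.** **Is there a stated fallback?** The relevant places, side by side:

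| Time point | Primary? | Setting in schedule | How the PCL-5 is obtained | Remote route stated? |
|---|---|---|---|---|
| T1 | yes | UniSC | emailed link before the visit (5.4) | yes |
| T3 | yes | UniSC | attended session, week 7 or 8 (5.4) | no |
| T4 | no | Telehealth | telehealth session (5.4) | yes |
| T5 | yes | UniSC | attended assessment (5.4) | no |

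Section 5.7 says only that staff may be present when self-rated scales are completed, so the instrument does not require attendance. The on-site sentence in section 5.9 does not fit T1 or T4.

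**Size.** The protocol gives no attendance rate, SD or expected change, so there is no figure to reproduce. What follows is illustration. The target of 150 is from section 5.2; the other inputs are assumptions.

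*Bias.* Let m be the share missing and g the shortfall in mean change of non-attenders relative to attenders, in SD units. The mean of observed data then overstates the mean of all participants by m × g.

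- m = 0.20, g = 0.25: 0.20 × 0.25 = 0.05 SD
- m = 0.20, g = 0.50: 0.20 × 0.50 = 0.10 SD
- m = 0.20, g = 1.00: 0.20 × 1.00 = 0.20 SD
- m = 0.40, g = 0.25 to 1.00: 0.10 to 0.40 SD

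*Bias after recovery.* With 20% missing, 120 attend and 30 do not. Suppose 15 of the 30 answer a link and resemble the other non-attenders. Non-attenders then make up 15/135 = 0.111 of the observed data instead of 0.20, so the overstatement is (0.20 − 0.111) × g = 0.089 g. That is 0.022 to 0.089 SD for g from 0.25 to 1.00. If instead the 15 who answer resemble attenders, the bias does not fall. The gain depends on who responds.

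*Precision.* The standard error ratio is √(120/135) = 0.943, a reduction of about 6%. For a paired change with 80% power and two-sided 5% significance, the detectable standardised change is (1.960 + 0.842)/√n:

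- n = 150: 0.229 SD
- n = 135: 0.241 SD
- n = 120: 0.256 SD

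The loss of precision is small. Possible selective loss is the larger issue.

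**The case against.** A reader might infer that the protocol has a rule under which the PCL-5 is forfeited when the visit is missed. It does not. The loss of a time point stands in the implications column of a general register, which also covers equipment that this study does not use. It describes what might happen, not how data will be handled. RC_10 also keeps inviting participants, promises a cancellation procedure that could include a remote route, and rates the likelihood of non-attendance as reduced once its controls are applied. All of this stands. What remains is that rescheduling is the only response now written down.

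The T1 column of the schedule has the same layout as T3 and T5, yet its PCL-5 is completed by link, so a place in that cell does not prove on-site completion. This is a fair point. However, the link sentence concerns the pre-treatment pack, nothing extends it to T3 or T5, and sections 5.4 and 5.9 point to attendance.

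A reader might also infer that missing data will fall on poor responders and favour the treatment. The documents do not show this: RC_10 lists traffic and personal factors among the causes too. Imputation could draw on the T2 and T4 PCL-5 and the weekly IES-R, which would reduce the bias computed above for observed data alone.

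Finally, a link does not recover the structured interview. Many people who stop treatment early would be lost through the exclusion wording in section 5.4 and the discontinuation criteria in section 5.5, not through the bundling of the visit. Both points limit what the change can achieve.

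**Conclusion.** The point holds as a gap in the collection plan. One of two primary instruments is planned for attended on-site sessions at both post-treatment primary time points, the only stated response to a missed visit is to rebook it, and a remote route already used at T1 and T4 is not carried over.

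The direction and size of any bias are assumptions. On those above, the observed mean would be 0.05 to 0.20 SD too favourable at 20% missing, less if imputation is informative, and zero if missing the visit is unrelated to change. The precision gain from recovering half of the missing forms is about 6% in the standard error. This is a cheap improvement worth making. It is not a flaw that invalidates the study.

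**What to change.** - **Section 5.4, T3 and T5:** send the PCL-5 link at the opening of each window to every participant who has not withdrawn consent, whether or not the on-site visit takes place. Add reminders, and record the date and mode of completion.
- **Appendix L, RC_10, or the pending cancellation procedure:** add the same step as a control. The implication column can stay as it is.
- **Section 5.9:** correct the on-site sentence so that it matches remote collection at T1 and T4, and now at T3 and T5.
- **Structured interview:** state that the link recovers the PCL-5 only. The interview could be offered by telehealth, as the T4 clinical interview already is.
- **Sections 5.4, 5.5 and 5.10:** reconcile follow-up of people who stopped treatment with the exclusion and discontinuation wording and with the intent-to-treat commitment. Without this, the link will not reach them.

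The cost is protocol wording, a Qualtrics distribution and minor staff time for reminders; no new instrument is needed. The downside is mixed completion mode within a time point, which is why the mode should be recorded.

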RC_14	Integrity of collected data is compromised.	An unauthorised person gaining access to data. Molecular biochemistry samples are compromised.	Integrity of the clinical trial is affected as data is compromised, reputation of Thompson Institute/UnISC can be impacted, affecting relationships in the community and future recruitment for clinical trials	Research Risk	Moderate	Possible	Medium	
 TI procedures and research protocols followed by TI staff when completing pathology request forms for blood collection. Research blood samples are collected and transported from in accordance with TI Management of Pathology SOP Clinical blood samples (if required) are collected and processed by private laboratory service, with copies of reports sent to the clinical research team and the participant's general practitioner. Research Pathology specimens stored in UnISC Lab which retains the integrity of the sample with oversight by TI Molecular Biologist (for quality control) 	Administrative	Effective	Director, Thompson Institute	Manager, Clinical Programs	Moderate	Unlikely	Medium	
RC_15	Location of participant is unknown	Participant leaves the TI and does not arrive at the expected location	Participant may have been affected by the treatment delivered, unfamiliar to surroundings, or missing, leading to loss of a participant, compromise to their safety and reputational damage to the TI	People Risk	Moderate	Possible	Medium	
 Contact details of participants and their Next of Kin are obtained at commencement of trial to ensure participants are well supported and an alternative person can be contacted in the event of an emergency Participants are informed to return to their accommodation or residence upon completion of treatment Participants that do not have someone to take them home or to their accommodation are provided a taxi voucher with Clinic staff ordering the taxi for the participant Participants are observed for a minimum time period (as identified in the research protocol) before leaving the TI and may be kept for longer for observation if still under the effects to the treatment medication. The identified time period has clinical significance for the after-effects of treatment Risk management plans are developed at the commencement of the study. 	Administrative	Effective	Director, Thompson Institute	Manager, Clinical Programs	Minor	Unlikely	Low	
TI_05	Fraud and corruption within the Thompson Institute	Staff spending money inappropriately, employment of contractors without due process, fabrication of qualifications, falsification of research data, conflicts of interest and input into research for publications.	Financial loss, reputational impact regulatory scrutiny, fines, loss of confidence	Operational Risk	Major	Possible	High	
 Financial approvals go through Institute Director and/or General Manager for review and sign off Credit card limits in place and there is a monthly review of transactions Responsible Officer Report from Finance reviewed by Institute Director and General Manager Conflicts of Interest - governing policy in place. Limited staff have access to Taxi account & password All staff complete mandatory GCP Research training. Staff follow UnISC Responsible Academic Research Conduct - Academic Policy. UnISC has a Compliance Management Framework in place. UnISC has Fraud and Corruption Control Policy and procedures in place 	Administrative	Effective	Director, Thompson Institute	Manager, Clinical Programs	Minor	Unlikely	Low	
TI_03	Loss of key staff	Key person risk, staff leaving and inadequate resources to continue research study or clinical trial, workforce retention issues. Staff absenteeism who are in critical roles and no backfill availability	Continuation or delay of research study or clinical trial, disruption to operational functions, loss of continuity for participants and clients	Research Risk	Major	Possible	High	
 Delegation of specific responsibilities and accountabilities in place Executive and management team who regularly meet formally Chief Investigator manages project specific procedures with relevant staff Regular team meetings to share research issues and findings Succession planning and considerations include: 
 Opportunities provided to TI staff to step up into more senior positions or take on additional responsibilities, provided it is within their skills, knowledge and capacity Ongoing recruitment of staff, including casual positions, to ensure minimal interruptions to business as usual due to staff absences. Ongoing engagement with key stakeholders and community organisations in an attempt to recruit additional key roles at the TI 	Administrative	Effective	Director, Thompson Institute	Manager, Clinical Programs	Major	Unlikely	Medium	

RC_21	Reputational Risk to the Thompson Institute and University of the Sunshine Coast	Ineffective delivery of Clinical Trials may lead to a poor perception of the Thompson Institute and/or the University of the Sunshine Coast	A poor reputation of the Thompson Institute or the University of the Sunshine Coast may lead to distrust of the community and a perception of poor use of public funds	Strategic/Growth Risk	Major	Unlikely	Medium	
 Clinical Trials have been developed by a number of experienced researchers All staff working the clinical trials have completed GCP Regular team meetings occur to evaluate the program and ensure program deliverables are being met All Staff are required to work within a defined Code of Conduct and in accordance with their professional responsibilities as a healthcare provider and/or employee of the University Graded notification to respective managers and executives on potential threats to the reputation of the TI and/or UniSC Standard Operating Procedures are in place to ensure staff are aware of responsibilities and processes in delivery of the program, providing a high quality program Utilisation of TI Communications and Marketing to ensure a good reputation is being delivered across the community 	Administrative	Effective	Director, Thompson Institute	Manager, Clinical Programs	Moderate	Rare	Low	

